## **10.9.2. Introduction for Substudy C**

### **10.9.2.1. Study Rationale**

Global health authorities have recommended a monovalent Omicron JN.1 lineage vaccine (such as JN.1 and KP.2) for the 2024-2025 season, and as a result, Cohorts 1 and 2 will study the safety, tolerability, and immunogenicity of BNT162b2 (Omi JN.1) and Cohort 3 will study the safety, tolerability, and immunogenicity of BNT162b2 (Omi KP.2).

Cohort 1: Based on protocol amendment 1, this initial and smaller segment of the substudy is intended to enable Pfizer/BioNTech to obtain early safety, tolerability, and immunogenicity data for up to 2 BNT162b2-based vaccines, each targeting a predominant circulating variant of SARS-CoV-2 in anticipation of the recommendation for the 2024-2025 variant-adapted vaccine by global health authorities. With the implementation of protocol amendment 2, Cohort 1 will be limited to the evaluation of BNT162b2 (Omi JN.1).

Cohort 2: In this second and larger segment of the substudy, Pfizer/BioNTech will evaluate the safety, tolerability, and immunogenicity of BNT162b2 (Omi JN.1).

Cohort 3: In this segment of the substudy, Pfizer/BioNTech will evaluate the safety, tolerability, and immunogenicity of BNT162b2 (Omi KP.2).

All 3 cohorts will enroll individuals who are either COVID-19 vaccine naïve or experienced, to reflect a real-world population. In addition, there is no requirement for vaccine-naïve participants to have had a positive SARS-CoV-2 test, considering that most people have already been exposed to COVID-19.

Refer to [Section 2.1](#) and [Section 2.2](#) for further details on the rationale for this substudy.

### **10.9.2.2. Background**

See [Section 2.2](#) for the study background.

### **10.9.2.3. Benefits/Risk Assessment**

No additional risks are identified for Substudy C beyond those detailed in [Section 2.3](#).

### **10.9.2.4. Benefit Assessment**

See [Section 2.3](#).

**10.9.3. Objectives, Estimands, and Endpoints for Substudy C**

Objectives	Estimands	Endpoints
Primary:	Primary:	Primary:
Safety		
Cohort 1 and Cohort 2 combined: To describe the safety and tolerability profile of BNT162b2 (Omi JN.1) 30 µg in participants ≥12 years of age.	In participants receiving 1 dose of study intervention, the percentage of participants reporting: 
 
Local reactions for up to 7 days following the study vaccination
 
Systemic events for up to 7 days following the study vaccination
 
AEs from the study vaccination through 1 month after the study vaccination
 
SAEs from the study vaccination through 6 months after the study vaccination
 
	
 
Local reactions (pain at the injection site, redness, and swelling)
 
Systemic events (fever, fatigue, headache, chills, vomiting, diarrhea, new or worsened muscle pain, and new or worsened joint pain)
 
AEs
 
SAEs
 

Cohort 3: To describe the safety and tolerability profile of BNT162b2 (Omi KP.2) 30 µg in participants ≥18 years of age.	In participants receiving 1 dose of study intervention, the percentage of participants reporting: 
 
Local reactions for up to 7 days following the study vaccination
 
Systemic events for up to 7 days following the study vaccination
 
AEs from the study vaccination through 1 month after the study vaccination
 
SAEs from the study vaccination through 6 months after the study vaccination
 
	
 
Local reactions (pain at the injection site, redness, and swelling)
 
Systemic events (fever, fatigue, headache, chills, vomiting, diarrhea, new or worsened muscle pain, and new or worsened joint pain)
 
AEs
 
SAEs
 

Immunogenicity		
Cohort 1 and Cohort 2 combined: To describe the immune response to BNT162b2 (Omi JN.1) 30 µg and BNT162b2 (Omi XBB.1.5) a 30 µg in participants ≥12 years of age.	In participants complying with the key protocol criteria (evaluable participants): 
 
GMT 1 month after vaccination
 
GMFR from before the study vaccination to 1 month after vaccination
 
Percentages of participants with seroresponseb 1 month after vaccination
 
	
 
SARS-CoV-2 Omi JN.1–neutralizing titers
 
SARS-CoV-2 Omi XBB.1.5–neutralizing titers
 

Cohort 3: To describe the immune response to BNT162b2 (Omi KP.2) 30 µg and BNT162b2 (Omi JN.1) c 30 µg in participants ≥18 years of age.	In participants complying with the key protocol criteria (evaluable participants): 
 
GMT 1 month after vaccination
 
GMFR from before the study vaccination to 1 month after vaccination
 
Percentages of participants with seroresponseb 1 month after vaccination
 
	
 
SARS-CoV-2 Omi KP.2–neutralizing titers
 
SARS-CoV-2 Omi JN.1–neutralizing titers
 

Objectives	Estimands	Endpoints
Exploratory:	Exploratory:	Exploratory:
Cohort 1 and Cohort 2 combined: To describe the immune response to BNT162b2 Omi (JN.1) d 30 µg and BNT162b2 (Omi XBB.1.5) a 30 µg in participants ≥12 years of age.	In participants complying with the key protocol criteria (evaluable participants): 
 
• GMT at each time point
 
• GMFR from before the study vaccination to each subsequent time point
 
• Percentages of participants with seroresponseb at each time point following vaccination for each variant-specific neutralizing titer
 
	
 
• SARS-CoV-2 Omi JN.1–neutralizing titers
 
• SARS-CoV-2 Omi XBB.1.5–neutralizing titers
 

Cohort 3: To describe the immune response to BNT162b2 (Omi KP.2) d 30 µg and BNT162b2 (Omi JN.1) c 30 µg in participants ≥18 years of age.	In participants complying with the key protocol criteria (evaluable participants): 
 
• GMT at each time point
 
• GMFR from before the study vaccination to each subsequent time point
 
• Percentages of participants with seroresponseb at each time point following vaccination for each variant-specific neutralizing titer
 
	
 
• SARS-CoV-2 Omi KP.2–neutralizing titers
 
• SARS-CoV-2 Omi JN.1–neutralizing titers
 

Cohort 1 and Cohort 2 combined: To describe confirmed COVID-19 and severe COVID-19 cases.		
 
• Confirmed COVID-19 cases
 
• Confirmed severe COVID-19 cases
 
• Strain sequencing of COVID-19 cases
 

Cohort 3: To describe confirmed COVID-19 and severe COVID-19 cases.		
 
• Confirmed COVID-19 cases
 
• Confirmed severe COVID-19 cases
 
• Strain sequencing of COVID-19 cases
 

Cohort 1 and Cohort 2 combined: To describe the immune response to emerging variants (under monitoring, of interest, and/or of concern). d		
 
• SARS-CoV-2–neutralizing titers for variants (under monitoring, of interest, and/or of concern) not already specified
 

Cohort 3: To describe the immune response to emerging variants (under monitoring, of interest, and/or of concern). d		
 
• SARS-CoV-2–neutralizing titers for variants (under monitoring, of interest, and/or of concern) not already specified
 

Objectives	Estimands	Endpoints
Cohort 2: To describe the cell-mediated immune response, and additional humoral immune response parameters, to the Omicron JN.1 strain in a subset of participants $\geq 18$ years of age with PBMC samples collected.		
Cohort 3: To describe the cell-mediated immune response, and additional humoral immune response parameters, to the Omicron KP.2 strain in a subset of participants with PBMC samples collected.		

- The participants from Substudy A will be used as a historical control for this objective, for the matched time points.
- Seroresponse is defined as achieving a  $\geq 4$ -fold rise from the baseline (before the study vaccination). If the baseline measurement is below the LLOQ, the postvaccination measure of  $\geq 4 \times \text{LLOQ}$  is considered seroresponse.
- The participants from Substudy C, Cohorts 1 and 2 combined, will be used as a historical control.
- Immunogenicity samples from a subset of participants may be tested for this objective.

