**Table 1. High-Level Overview of Substudies in Protocol for Variant-Adapted BNT162b2**

Phase	Group/Age	Dose Level	Number of Doses Administered Prior to Enrollment	Days From Last Prior Dose to Study Vax	Number of Doses to Be Administered During Study	Approximate Number of Participants
Substudy A: Evaluation of BNT162b2 (Omi XBB.1.5) in COVID-19 vaccine-experienced participants ≥12 years of age						
2/3	12-55 Years a	30 µg	≥3 b	≥150	1	200
	>55 Years					200
Substudy B: Evaluation of BNT162b2 (Omi XBB.1.5) as a single dose in participants ≥12 years of age who were previously exposed to SARS-CoV-2 and are COVID-19 vaccine naïve						
2/3	≥12 Years	30 µg	0	N/A	1	300
Substudy C – Cohort 1: Evaluation of BNT162b2 (Omi JN.1) as a single dose in participants ≥18 years of age						
2/3	18-55 Years	30 µg	≥0 c	≥150 (if applicable)	1	25
	>55 Years					25
Substudy C – Cohort 2: Evaluation of BNT162b2 (Omi JN.1) as a single dose in participants ≥12 years of age						
2/3	≥12 Years a	30 µg	≥0 c	≥150 (if applicable)	1	150
Substudy C – Cohort 3: Evaluation of BNT162b2 (Omi KP.2) as a single dose in participants ≥18 years of age						
2/3	18-55 Years	30 µg	≥0 c	≥150 (if applicable)	1	50
	>55 Years					50

- A maximum of 20 participants aged 12 through 17 years to be enrolled.
- Prior doses of a US-authorized mRNA COVID-19 vaccine, with the most recent dose being an Omicron BA.4/BA.5–adapted bivalent vaccine.
- Participants may be COVID-19 vaccine naïve or experienced, with any number of prior doses of any COVID-19 vaccine.

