**Table 14. Substudy C Design: Cohort 2**

Open-Label				
Group	Study Intervention	Study Dose	Participant Age Group	Number of Participants
1	BNT162b2 (Omi JN.1)	30 µg	12-55 Years	75 a
			>55 Years	75

- a. A maximum of 20 participants 12 through 17 years of age will be enrolled. If fewer than 20 participants are enrolled in this age group, the difference will be added to the number of participants enrolled in the 18-through 55-year age group.

Cohort 3 will enroll participants  $\geq 18$  years of age who will receive a single open-label 30- $\mu\text{g}$  dose of BNT162b2 (Omi KP.2), which targets the SARS-CoV-2 variant Omicron KP.2. Approximately 100 participants will be enrolled. The study duration will be approximately 6 months, with 6 scheduled visits. Reactogenicity e-diaries will be used to collect prespecified local reaction and systemic event data during the 7-day collection period, or longer for ongoing symptoms, after study intervention (ie, from Day 1, the day of vaccination, until symptom resolution). The active collection period for AEs will be through approximately 1 month after vaccination and for SAEs through approximately 6 months after vaccination. COVID-19 surveillance will be conducted throughout the study. Blood samples will be taken at each visit for all participants for assessment of immunogenicity. A subset of approximately 20 participants each in the 18- through 55-year and  $>55$ -year age groups who consent to collection of optional additional blood samples will comprise the PBMC subset for exploratory evaluation of B- and T-cell responses and HLA typing.

Participants from Study C4591054 – Substudy C, Cohorts 1 and 2 combined, who received BNT162b2 (Omi JN.1) 30  $\mu\text{g}$  will be used as a control group for immunogenicity assessment of BNT162b2 (Omi KP.2).

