Cohort 2: To describe the cell-mediated immune response, and additional humoral immune response parameters, to the Omicron JN.1 strain in a subset of participants ≥ 18 years of age with PBMC samples collected.		
Cohort 3: To describe the cell-mediated immune response, and additional humoral immune response parameters, to the Omicron KP.2 strain in a subset of participants with PBMC samples collected.		

- The participants from Substudy A will be used as a historical control for this objective, for the matched time points.
- Seroresponse is defined as achieving a ≥ 4 -fold rise from baseline (before the study vaccination). If the baseline measurement is below the LLOQ, the postvaccination measure of $\geq 4 \times$ LLOQ is considered seroresponse.
- The participants from Substudy C Cohort 1 and Cohort 2 combined will be used as a historical control.
- Immunogenicity samples from a subset of participants may be tested for this objective.

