6.1.2.2.1. Main Analysis

- Estimands:
 - GMTs of SARS-CoV-2 Omi KP.2–neutralizing titers and SARS-CoV-2 Omi JN.1–neutralizing titers at 1 month after vaccination for each age subgroup (18-55 years, >55 years) and overall.
 - GMFRs of SARS-CoV-2 Omi KP.2–neutralizing titers and SARS-CoV-2 Omi JN.1–neutralizing titers from before the study vaccination to 1 month after the study vaccination for each age subgroup (18-55 years, >55 years) and overall.
 - Percentages of participants with seroresponse to SARS-CoV-2 Omi KP.2 and SARS-CoV-2 Omi JN.1 at 1 month after vaccination for each age subgroup (18-55 years, >55 years) and overall.
- Analysis sets: Evaluable immunogenicity population, all-available immunogenicity population (as applicable) ([Section 4](#)).
- Analysis time points: 1 Month after vaccination, from before the study vaccination to 1 month after the study vaccination (for GMFRs only).
- Analysis methodology: The GMTs and the associated 2-sided 95% CIs at 1 month after the study vaccination will be provided using the statistical methods described in [Section 5.2.3](#). The GMFRs and the associated 2-sided 95% CIs from before the study vaccination to 1 month after the study vaccination will be provided using the statistical methods described in [Section 5.2.4](#). The percentages of participants with seroresponse at 1 month after the study vaccination and the associated Clopper-Pearson 95% CIs will be provided ([Section 5.2.1](#)). Seroresponse is defined as achieving a ≥ 4 -fold rise from baseline (before the study vaccination). If the baseline measurement is below the LLOQ, the postvaccination measure of $\geq 4 \times \text{LLOQ}$ is considered seroresponse.
- Intercurrent events and missing data: Serology data deemed unevaluable because of noncompliance with the key protocol criteria will be excluded. Missing data will not be imputed.

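### The JN.1 control for Cohort 3 carries no adult restriction, so its overall row, read literally, covers a wider age range than the objective for participants 18 and older

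*Protocol*

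**What the plan says.** **Objective.** In the protocol's Section 10.9.3 table, the Cohort 3 primary immunogenicity objective names both vaccines and limits the population: "30 µg in participants ≥18 years of age". The Cohort 3 exploratory immunogenicity objective has the same limit. Table 1 gives the matching eligibility: "Substudy C – Cohort 3: Evaluation of BNT162b2 (Omi KP.2) as a single dose in participants ≥18 years of age".

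**Control.** Footnote c of that table reads "The participants from Substudy C, Cohorts 1 and 2 combined, will be used as a historical control". Footnote c of Table 2 in the Substudy C SAP says the same: "The participants from Substudy C Cohort 1 and Cohort 2 combined will be used as a historical control". The protocol synopsis, Sections 10.9.4.1, 10.9.4.3, 10.9.9.3.2 and 10.9.9.3.3, and SAP Sections 2.3 and 6.1.2.2 also name Cohorts 1 and 2. None of them adds an age limit.

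**Who is in that control.** Table 1 describes the larger contributing cohort as "Substudy C – Cohort 2: Evaluation of BNT162b2 (Omi JN.1) as a single dose in participants ≥12 years of age". Table 14 caps the adolescents: "A maximum of 20 participants 12 through 17 years of age will be enrolled".

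**What is reported.** The SAP's Cohort 3 estimands are given "at 1 month after vaccination for each age subgroup (18-55 years, >55 years) and overall". Neither document says which JN.1 recipients make up the overall row.

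**The concern.** The objective and its control are defined on different age ranges. A programmer who follows the control definition puts 12-17-year-olds into the overall JN.1 row. One who follows the objective leaves them out. The two choices give different numbers for a primary descriptive display, and only the second answers the stated adult objective. In the first, a reader comparing the overall KP.2 and JN.1 rows sees adults on one side and a mixed-age group on the other.

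The choice should be settled in advance. Protocol Section 10.9.9.4 lets the sponsor review unblinded data while the study runs, and the Amendment 2 rationale states that Cohorts 1 and 2 were already enrolled when Cohort 3 was added. An undefined overall row can therefore be resolved after JN.1 results have been seen.

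**Working it through.** **Inputs**
- Cohort 1, JN.1 (protocol Table 13): 25 aged 18-55 and 25 aged >55.
- Cohort 2, JN.1 (Table 14): 75 aged 12-55, of whom at most 20 are aged 12-17, and 75 aged >55.
- Cohort 3, KP.2 (Table 15): 50 aged 18-55 and 50 aged >55.
- Adolescent-to-adult GMT ratio *r*: not in the documents; an assumed range is used.

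**1. The plan's own total.** 25 + 25 + 75 + 75 = 200, which agrees with the total of JN.1 recipients stated in Section 10.9.4.1.

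**2. Age make-up with all 20 adolescents enrolled**

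| Age | JN.1 control, unrestricted | JN.1 control, 18 and over | Cohort 3 |
|---|---|---|---|
| 12-17 | 20 (10%) | 0 | 0 |
| 18-55 | 25 + 75 - 20 = 80 (40%) | 80 (44.4%) | 50 (50%) |
| >55 | 25 + 75 = 100 (50%) | 100 (55.6%) | 50 (50%) |
| Total | 200 | 180 | 100 |

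Adolescents are 20/200 = 10% of the planned control and 20/150 = 13.3% of Cohort 2.

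**3. Effect on the overall control GMT.** A GMT is the exponential of a mean log titer. Adding a 10% share whose GMT is *r* times the adult GMT multiplies the overall GMT by *r*^(20/200) = *r*^0.10.

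| Assumed *r* | Multiplier on overall JN.1 GMT |
|---|---|
| 0.5 | 0.933 |
| 0.67 | 0.961 |
| 1 | 1.000 |
| 1.5 | 1.041 |
| 2 | 1.072 |

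**4. Effect on the overall seroresponse rate.** The shift is 0.10 times the adolescent-adult difference. An assumed difference of ±10 to ±20 percentage points moves the overall rate by ±1 to ±2 points.

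**5. Precision lost by restricting to adults.** The 95% CI factor for a single-group GMT is exp(1.96 × SD/√n). The documents give no SD for Substudy C. Borrowing the log-scale 1.35 from the Substudy B sample size section, and treating everyone enrolled as evaluable, the factor is 1.206 at n = 200 and 1.218 at n = 180.

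**6. Side effect of the restriction.** The adult control would be 55.6% aged >55, against 50% in Cohort 3. If the >55 GMT is *R* times the 18-55 GMT, this difference in mix multiplies the control's overall GMT by *R*^(0.556 - 0.50) = *R*^0.056. Protocol Section 2.2.1 gives Substudy A postvaccination GMT ranges across strains of 559.3-732.3 (>55) and 370.3-444.4 (18-55). Dividing like ends gives 559.3/370.3 = 1.51 and 732.3/444.4 = 1.65. With *R* of about 1.5 to 1.65 as an illustration, the multiplier is 1.02 to 1.03.

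**The case against.** The best reply is that adults are plainly meant. The objective limits both responses to age 18 and over. The SAP adds a 12-17 subgroup, marked as Cohort 2 only, where adolescents belong, and leaves it out of the Cohort 3 estimands. On that view the overall row is simply the sum of the two adult subgroups. The reading is reasonable, and it shows that the documents do not expressly instruct anyone to include adolescents. It does not settle the matter, because every definition of the control says otherwise when read literally. The documents do state age limits where they want them, as in the Cohort 2 cell-mediated objective.

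A second reply is that the effect is small and the analysis descriptive. Both are true. Twenty is a ceiling, any shortfall is filled by 18-55-year-olds, and the adult subgroup rows do not change.

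A third reply is that the filter disturbs a balance. With adolescents included, the control is split evenly at age 55, as Cohort 3 is; without them it is 44/56. If adolescents respond like 18-55-year-olds, the filter moves the overall control GMT about 2-3% away from Cohort 3's mix. This stands as a caution about how the overall row is read. It is no reason to keep participants whom the objective excludes.

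**Conclusion.** The mismatch is real and modest. Applied as written, the control definition lets up to 10% of the overall JN.1 row come from an age group outside the Cohort 3 objective. Over an assumed *r* of 0.5 to 2, the overall control GMT is multiplied by about 0.93 to 1.07. This takes all 20 adolescents as enrolled and as evaluable as the adults.

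Three stronger readings are not supported:

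- **That adolescents inflate the JN.1 control and so disadvantage KP.2.** No adolescent titers are given. The only age contrast cited is between two adult groups, with the older one higher, and it says nothing about ages 12-17.
- **That a formal KP.2-to-JN.1 comparison is biased.** Substudy C has no hypothesis test, and its SAP plans no between-vaccine ratio. GMTs, fold rises and seroresponse are reported for each group.
- **That the Cohort 3 objective cannot be answered.** The 18-55 and >55 rows are planned and already restricted to adults on both sides.

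**What to change.** Define the Cohort 3 control as participants 18 years of age and older from Substudy C Cohorts 1 and 2 combined.

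- **Substudy C SAP, now:** Table 2 footnote c, Section 2.3 and Section 6.1.2.2. Section 6.4.1.2 follows by reference. Section 2.1, which currently declares no departures from the protocol, should record the change until the protocol is aligned.
- **Protocol, at the next amendment:** the synopsis, Section 10.9.3 footnote c, and Sections 10.9.4.1, 10.9.4.3, 10.9.9.3.2 and 10.9.9.3.3. Section 9 allows the SAP to modify the protocol's analysis outline, so a separate amendment for this alone should not be needed.
- **Reporting:** present the 18-55 and >55 rows first, or weight the overall JN.1 row to Cohort 3's age mix.

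The cost is a phrase in each place and one filter in the program. At least 180 planned controls remain, with little loss of precision. The remaining downside is the 44/56 adult age mix, which the reporting step deals with.

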#### 10.9.4. Study Design for Substudy C

##### 10.9.4.1. Overall Study Design

This is a Phase 2/3 open-label study to evaluate the safety, tolerability, and immunogenicity of 2 BNT162b2-based vaccines, each targeting a predominant circulating variant of SARS-CoV-2. The substudy will be divided into 3 cohorts.

Cohort 1 will enroll approximately 50 participants 18 years of age and older (approximately 25 participants each in the 18- through 55-year and  $>55$ -year age groups), who will receive a single 30- $\mu\text{g}$  dose of BNT162b2 (Omi JN.1). The study duration will be approximately 6 months, with 6 scheduled visits. Reactogenicity e-diaries will be used to collect prespecified local reaction and systemic event data during the 7-day collection period, or longer for ongoing symptoms, after study intervention (ie, from Day 1, the day of vaccination, until symptom resolution). The active collection period for AEs will be through approximately 1 month after vaccination and for SAEs through approximately 6 months after vaccination. COVID-19 surveillance will be conducted throughout the study. Blood samples will be taken at each visit for all participants for assessment of immunogenicity.

Participants from Study C4591054 – Substudy A who received BNT162b2 (Omi XBB.1.5) 30  $\mu\text{g}$  will be used as a control group for immunogenicity, for the matched time points.

**Table 13. Substudy C Design: Cohort 1**

Open-Label				
Group	Study Intervention	Study Dose	Participant Age Group	Number of Participants
1	BNT162b2 (Omi JN.1)	30 µg	18-55 Years	25
			>55 Years	25

Cohort 2 will enroll participants  $\geq 12$  years of age who will receive a single open-label 30-µg dose of BNT162b2 (Omi JN.1). Enrollment into Cohort 2 will begin once Cohort 1 has completed enrollment. Approximately 150 participants will be enrolled into Cohort 2, resulting in a total of 200 participants receiving BNT162b2 (Omi JN.1) (including the 50 participants from Cohort 1). The study duration will be approximately 6 months, with 5 scheduled visits (no 2-week visit). Reactogenicity e-diaries will be used to collect prespecified local reaction and systemic event data during the 7-day collection period, or longer for ongoing symptoms, after study intervention (ie, from Day 1, the day of vaccination, until symptom resolution). The active collection period for AEs will be through approximately 1 month after vaccination and for SAEs through approximately 6 months after vaccination. COVID-19 surveillance will be conducted throughout the study. Blood samples will be taken at each visit for all participants for assessment of immunogenicity. A subset of approximately 30 participants each in the 18- through 55-year and >55-year age groups who consent to collection of optional additional blood samples will comprise the PBMC subset for exploratory evaluation of B- and T-cell responses and HLA typing.

For both cohorts, participants from Study C4591054 – Substudy A who received BNT162b2 (Omi XBB.1.5) 30 µg will be used as a control group for immunogenicity assessment (for the matched time points).

